Official Title: Duration of Brace Wear in Clubfoot Treatment – A Prospective Randomized Trial

NCT Number: NCT01551264

Document Date: December 30, 2011

Duration of Brace Wear in Clubfoot Treatment – A Prospective Randomized Trial

RESEARCH DESIGN AND METHODS

Aim 1

- a. Establish the time dependent risk for relapse with need for further therapy in isolated clubfoot for 2 year versus 4 year bracing.
- b. Determine whether covariates that include compliance with bracing, gender, age, severity, and family history are associated with relapse.

Rationale

Based on the hypothesis that prolonged bracing will reduce clubfoot recurrence, we propose a multi-center, randomized, controlled trial evaluating the effectiveness of a 2 year versus 4 year bracing protocol in preventing clubfoot recurrence. No studies have previously assessed the length of bracing necessary to prevent clubfoot recurrence; therefore, the results of this study will have great clinical utility. When designing this trial, we sought to balance rigor with feasibility, and to maximize internal validity without sacrificing external validity.

Sample Size Justification and Statistical Power

The primary goal of this project is to determine the rate at which clubfoot recurs during the first year post-treatment. Because this primary goal involves estimation, we discuss sample size issues from the perspective of confidence bounds. *Table 1 presents the statistical power to detect between-group differences for various recurrence rates with the target enrollment sample size of 62 patients per group. Assuming a 10% dropout rate, with a total enrollment of 124 patients (55/group completing the entire trial) and observed recurrence rates of 10% versus 45%, statistical power will be excellent (0.99) to detect this between-group difference in recurrence rate of at least 35%.* That is, with 95% certainty, our estimate of the between-group difference in recurrence rate will be within 15% (50%-20%/2) of the true rate difference. Even with a more conservative estimate of the between-group difference, the study will have adequate power (0.80) to detect a between-group difference as small as 21%; where the recurrence rate in one group is 10% and the recurrence rate in the other group is as small as 31%.

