Two comments about the above computations are in order. First, we have estimated confidence bound widths using proportions instead of the Kaplan-Meier survival curves we will use in practice when we analyze the data. The reason is that we have no way at this time to estimate the standard errors that will result from the survival curves. During the early portions of the curve when we have complete data, we anticipate that the confidence bounds generated by the survival curves will be narrower than those presented above. By contrast, it is possible that the confidence bounds we generate for later portions of the curve may be wider than those presented above given the presumed number of dropouts. Second, we believe that independent of the standard errors resulting from the survival curves, our computed confidence bound widths are inherently conservative (i.e. we may get

narrower bounds in practice). The reason is that we anticipate in practice that the true dropout rate, particularly at earlier time points, will be less than the 10% that has been used in computing the number of subjects who provide data. Study dropouts will increase the study power because they will provide useful data up to the point of dropout. Thus, we believe that the presented power computations based on the sample of patients that complete the trial are conservative.

In addition to the reasons already presented, the provided power computations ensure a conservative estimate of sample size because they (1) utilize reoccurrence rates through 12 months of follow-up data only, and more patients will reoccur over time, and (2) have been performed using a dichotomous outcome measure whereas the data will be analyzed using survival analysis where follow-up on many patients will exceed 12 months. The primary analysis will enhance power by applying survival models and using a log rank test to compare time to reoccurrence between treatment groups.

Table 1. Recurrence rate between-group differences detectable with alternative incidences and a target enrollment of 124 patients (62 per group). Estimates based on two-tailed tests at alpha=0.05 comparing the rate of the event in two groups.

# of Patients in each Group		Detectable Relapse Rate at Specified Sample Size and Power			Power
Enrolled	With Complete Data*	Group 1	Group 2	Between-Group Difference (95% CI)	
62	55	10%	45%	35% (20%, 50%)	0.99
			40%	30% (15%, 45%)	0.96
			31%	21% (6%, 36%)	0.80

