Randomization will be stratified by sex (male/female) and laterality (unilateral/bilateral) within each clinical site. Within each stratum, patients will be allocated in a 1:1 ratio to either 2-year or 4-year bracing using a variable block size to ensure that there is no temporal bias and that the two study arms will be balanced by gender and laterality within each site. Randomization sequences will be generated with SAS software (SAS Institute Inc., Cary, NC, USA) by the study statistician *a priori*. When a participant is ready to be randomized, the site coordinator will access a secure and password-protected website, provide the participant's study ID number, identify the appropriate stratum, and verify that the participant fulfills the eligibility requirements. The website will then access the randomization sequence for that stratum, determine the next treatment assignment, and elicit the treatment assignment. A study subject will be randomized and assigned to treatment only when it has been determined that he/she has satisfied all the eligibility requirements for the study and informed consent for the intervention phase has been obtained.

To ensure that we are collecting quality data, we developed valid and logically consistent case report forms that will be used in these studies. Clinical information includes severity (Pirani score), age at treatment initiation, sex, laterality, family history of clubfoot in first degree relative, number of casts required to treat, use of tenotomy, and the presence of the drop toe sign (Edmonds and Frick 2009). Individuals collecting and entering data will be adequately trained, and data will be monitored to ensure that the database is accurate.

The coordinator will download the data from the dose monitor at each 3-month visit, and re-launch it so it can be remounted by the orthotist. The data will be saved as a comma delimited file and the file will be uploaded into the data entry system by the site coordinator..

3. Casting and Bracing Protocol

The Ponseti method of casting will be followed and all PI's are Ponseti certified physicians. Tenotomy will be performed before last cast application for any foot that cannot achieve at least 10° of ankle dorsiflexion as measured with a hand-held goniometer. The foot will be considered corrected if greater than 50° of foot abduction and greater than 10° of ankle dorsiflexion can be achieved, both measured with hand-held goniometer. Those feet that

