Study subjects will be seen every 3 months. Interim visits for brace fitting and consultation or family discussions with the physician/coordinator/orthotist will be allowed and encouraged. Local coordinators will contact the patient and family via phone at least monthly to provide the opportunity for questions, discussion, and feedback as needed. Subjects will be evaluated at each visit of the current state of their clubfoot and will be told if there are any signs of recurrence. Parents have the right to withdraw from the study at anytime.

5. Study Endpoint

Although follow-up data will be collected for the duration of the trial, the data collected at 1-year follow-up post completion of treatment arms will be used for the primary analysis to address the question asked in specific aim 1a. This ensures that patients in both treatment arms are followed for the same amount of time after they finish bracing.

6. Statistical Analysis

General

The goal of this study is to establish the time-dependent risk for recurrence within the first year post-treatment and evaluate factors associated with recurrence in isolated clubfoot. Kaplan-Meier survival curves that describe the time to recurrence will be generated, with

95% confidence bounds placed around the probabilities that this event will occur at pre-defined intervals. Of particular interest will be an assessment of the hazard ratio, with 95% confidence bounds, that compares recurrence in patients receiving 2-year versus 4-year bracing. While the goal of this study is to detect an overall treatment difference, Cox regression analysis will determine whether covariates that include compliance with bracing, gender, laterality, age, Pirani score, and family history are associated with the probability that relapse will occur. A separate Cox model will be used for each covariate.

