Additional analyses include mixed model repeated measures analysis of variance to determine if the magnitude of changes in exam findings differs according to whether a recurrence ultimately occurs. Unlike traditional repeated measures analyses, the mixed model method allows for the inclusion of patients with incomplete data. The focus of these analyses will be the interaction between recurrence group and time point; interactions that test hypotheses regarding the equality of changes over time in the two groups. Within the mixed model, appropriate statistical contrasts will be used to test the null hypothesis that changes between two specific time points in one group are equal to corresponding changes in another group.

Simple t-tests and chi-square tests will be used to determine if characteristics at study enrollment differ according to whether there is recurrence. Receiver operating characteristic (ROC) curve analysis will be performed to determine if measures of compliance discriminate patients that recurrence from patients that do not recurrence.

These data will be analyzed with an "intention to treat" principle; wherein patients will be included in the intervention group as determined by the randomization, independent of compliance. Secondary analyses will be performed to evaluate the effects of treatment independent of crossover by examining outcomes relative to actual treatment status.

For all analyses, careful attention will be given to whether the data satisfy the distributional and model-specific assumptions of the procedures used. Appropriate data transformations or non-parametric methods will be used as appropriate.

It is important to point out that this study is not designed to (1) assess the safety or efficacy of a particular brace; (2) compare outcomes across clinical sites. All sites will use foot abduction braces. To avoid any perception of conflict of interest and to follow recommendations from the Disclosure Review Committee, the type of particular brace used will not be recorded in the study data. Brace type is inherently associated with clinical site and site physician. As such, the following variables will not be included as effects of interest in the analytic models: brace type, clinical site, physician, and orthotist.

Heat sensor data (analysis)

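### The primary log-rank test and hazard ratio name no strata although randomisation is stratified by sex and laterality within site: valid, but naming a sex-by-laterality stratified analysis in advance is a cheap improvement

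*Combined protocol and SAP*

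**What the plan says.** Section 2, Randomization and Data Collection, states: "Randomization will be stratified by sex (male/female) and laterality (unilateral/bilateral) within each clinical site". Allocation is 1:1 with variable block sizes inside each stratum. With seven centres this gives 7 x 2 x 2 = 28 randomisation cells.

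Sample Size Justification and Statistical Power names the primary test, "using a log rank test to compare time to reoccurrence between treatment groups". Section 6, Statistical Analysis (General), adds the effect measure: "an assessment of the hazard ratio, with 95% confidence bounds, that compares recurrence in patients receiving 2-year versus 4-year bracing". Neither sentence mentions strata or adjustment.

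Sex and laterality return in section 6, in a sentence that begins "While the goal of this study is to detect an overall treatment difference" and then turns to Cox models for whether "covariates that include compliance with bracing, gender, laterality, age, Pirani score, and family history are associated with the probability that relapse will occur", one model per covariate. The overall comparison is thus set apart from the models that contain these factors. Section 6 also says that "the following variables will not be included as effects of interest in the analytic models: brace type, clinical site, physician, and orthotist".

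**The concern.** The design forces balance on two factors that the plan itself treats as possible predictors of relapse. When such factors are prognostic, the balance makes the true variance of the log-rank score smaller than the unstratified formula assumes. The test then rejects less often than 5% under the null and gives up some power. A test stratified by the same factors recovers this.

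At the smallest difference in Table 1 there is little power to spare: 0.80, with about 23 expected events. The text also leaves the choice of primary test open. In simulation the stratified and unstratified tests reach different verdicts in up to 5% of trials, so the choice is better made before data are seen.

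**Working it through.** **Inputs from the documents.** Two-sided alpha 0.05; 62 enrolled and 55 completing per arm; recurrence of 10% versus 45%, 40% or 31%, with stated power 0.99, 0.96 and 0.80 (Table 1); seven sites; 1:1 blocks within site x sex x laterality.

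**Assumed, because the documents give no figure.** The prognostic hazard ratios (HRs) for sex and laterality, the shares of boys and of bilateral cases, equal site sizes, and the spread of site effects.

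**1. The plan's own power.** For two proportions with pooled null variance, power = Φ[(d - 1.96·√(2·p̄·(1-p̄)/n)) / √((p1(1-p1)+p2(1-p2))/n)]. With n = 55, p1 = 0.10, p2 = 0.31:

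- d = 0.21 and p̄ = 0.205
- null SE = √(2 x 0.205 x 0.795/55) = 0.0770
- alternative SE = √((0.0900 + 0.2139)/55) = 0.0743
- power = Φ[(0.21 - 0.1509)/0.0743] = 0.787 (the arcsine formula gives 0.805)

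The other rows give 0.990 and 0.963. Enrolment is 55/0.90 = 61.1, rounded up to 62. The stated figures reproduce, and none depends on stratification.

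**2. Sparsity.** Expected events at 10% versus 31% are 55 x (0.10 + 0.31) = 22.6. Over 28 cells that is 124/28 = 4.4 patients and 22.6/28 = 0.8 events per cell. Over 4 strata it is 124/4 = 31 patients and 22.6/4 = 5.6 events on average.

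**3. Power at 10% versus 31%.** There are two simulations with exponential times over 12 months, calibrated so that the marginal risks stay at 10% and 31%.

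- Simulation A: 20,000 trials per scenario, 110 completers, 65% male, 50% bilateral.
- Simulation B: 8,000 trials per scenario, 124 patients with 10% dropping out during the year, two thirds male, half bilateral.

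There is no site effect in this table. Changes are in percentage points, taken before rounding.

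| HR for sex, laterality | A: unstratified | A: 4 strata | Change | B: unstratified | B: 4 strata | Change |
|---|---|---|---|---|---|---|
| 1, 1 | 0.803 | 0.798 | -0.5 | 0.830 | 0.828 | -0.2 |
| 1.5, 1.5 | 0.802 | 0.802 | 0.0 | 0.829 | 0.830 | +0.1 |
| 1.5, 2 | 0.808 | 0.812 | +0.3 | | | |
| 2, 2 | 0.801 | 0.811 | +1.0 | 0.836 | 0.848 | +1.2 |
| 2, 3 | 0.803 | 0.823 | +2.0 | | | |
| 3, 3 | 0.811 | 0.839 | +2.8 | 0.847 | 0.871 | +2.5 |

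B has higher power throughout because dropouts contribute time until they leave. The paired changes agree. With other sex and laterality splits, A ranges from -0.8 (no effect) to +3.3 (3, 3). A smaller run of 3,000 trials gave about -1.0 with no effect, +0.6 at 2, 2 and +2.5 at 3, 3.

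**4. The other rows of Table 1.** A run of 6,000 trials gave, unstratified versus 4 strata:

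- 10% versus 45%: 0.992 vs 0.990 (no effect), 0.992 vs 0.994 (2, 2), 0.994 vs 0.996 (3, 3)
- 10% versus 40%: 0.970 vs 0.968, 0.975 vs 0.979, 0.973 vs 0.984

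**5. Type I error.** The null risk is 20.5% in both arms in A and 31% in both arms in B.

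| HR for sex, laterality; site SD (log hazard) | Simulation | Unstratified | 4 strata |
|---|---|---|---|
| 1, 1; 0 | A | 0.051 | 0.051 |
| 1, 1; 0 | B | 0.056 | 0.057 |
| 2, 2; 0 | B | 0.045 | 0.051 |
| 2, 3; 0 | A | 0.043 | 0.050 |
| 3, 3; 0 | A | 0.044 | 0.050 |
| 3, 3; 0 | B | 0.039 | 0.052 |
| 2, 2; 0.5 | B | 0.037 | 0.041 |
| 2, 3; 0.5 | A | 0.040 | 0.047 |
| 3, 3; 0.8 | A | 0.033 | 0.039 |

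The 0.056 in B is about 2.5 Monte Carlo standard errors above 0.05 ((0.056 - 0.050)/0.0024). The stratified test shows the same excess, so the choice of strata does not cause it.

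**6. All 28 cells.** With no prognostic effect, power falls to 0.746 in A (5.7 points below unstratified) and 0.793 in B (3.7 below). It is below the 4-stratum test in every scenario run. In A, 1.6 of 22.6 events (7.2%) occur when only one arm is still at risk in the cell, and such events carry no information on treatment. With 4 strata this is under 0.01%.

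**7. Estimation.** In A the median SE of the log hazard ratio, unstratified versus 4 strata, is 0.500 vs 0.503 with no effect, 0.500 vs 0.502 at 2, 3 and 0.500 vs 0.503 at 3, 3. The median hazard ratio is 3.58 vs 3.58, 3.54 vs 3.72 and 3.60 vs 3.84. The two tests give the same verdict in 95.0% to 97.3% of trials.

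**The case against.** The strongest reply is that this is a preference between two valid tests, and much of it stands.

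- **No error.** The text is silent on strata and contradicts nothing. This stands.
- **The benefit rests on assumed effects.** The documents give no prognostic effect for sex or laterality; they list both only as associations to be tested, and Aim 1b does not name laterality. The one factor described as a leading risk (section 6, Heat sensor data) is brace noncompliance, which is measured after randomisation. This stands: even the sign of the benefit is uncertain.
- **The gain appears mainly in the least favourable row of Table 1.** This stands. At 10% versus 45% the change is about 0.2 points either way.
- **The remedy does little for the stated goal.** The sample size section says "Because this primary goal involves estimation, we discuss sample size issues from the perspective of confidence bounds", and section 6 says "Kaplan-Meier survival curves that describe the time to recurrence will be generated". The stratified hazard ratio is no more precise and no longer matches the marginal curves directly. This stands, and is why the unstratified results should be kept.
- **Four strata do not remove all the conservatism.** This stands too. Site is also a randomisation stratum; at 2, 2 with site SD 0.5, type I error moves only from 0.037 to 0.041, against 0.050 with 28 strata.

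A reader might also infer that section 6 requires site to be left out of the strata. It does not: it bars site as an effect to be estimated, and a stratification variable is not estimated. The reason to leave site out is that the cells are too sparse.

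What survives is that the plan does not say which analysis is primary, and saying so costs nothing.

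**Conclusion.** A cheap improvement, of the lowest severity. Read plainly, the primary test and hazard ratio ignore the factors used to stratify randomisation. A reader might infer that the test is therefore invalid, that it inflates false positives, or that the power in Table 1 is wrong. None of these holds: ignoring balanced prognostic factors makes the test conservative, and the stated power reproduces without reference to strata.

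The size is conditional. At 10% versus 31%, four strata cost about 0.2 to 1 point of power if neither factor is prognostic, change nothing at 1.5 each, and gain about 1 point at 2 each and 2.5 to 3 points at 3 each. The change is negligible at 10% versus 45%. All prognostic and site effects here are assumptions, and the documents support no particular value. Conservatism due to site would mostly remain.

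**What to change.** State in section 6, before any comparison by arm:

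1. The primary test is a two-sided 0.05 log-rank test stratified by sex x laterality (4 strata), using the values recorded at randomisation.
2. The hazard ratio and its 95% confidence interval come from a Cox model stratified in the same way, and are labelled as conditional on sex and laterality.
3. The unstratified log-rank test and hazard ratio are reported as a sensitivity analysis, beside the marginal Kaplan-Meier curves already planned.
4. Site is left out of the strata because the 28 cells are too sparse.

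If the investigators prefer the unstratified test as primary, the plan should say so explicitly.

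The cost is wording only: both factors are already collected, and the sample size and Table 1 do not change. The downsides are up to about 1 point of power if the factors are not prognostic, a hazard ratio somewhat further from 1 than the marginal one when they are (3.54 to 3.72 at 2 and 3), and no gain in the width of its confidence interval.

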are not fully corrected will undergo further casting until correction is achieved before starting the bracing protocol. The number of casts required to achieve correction will be recorded as well as any casting complications. After achieving correction all patients are fitted **with a foot abduction brace (FAB) consisting of shoes attached to a bar**. The type of FAB used will be based on physician and family preference but the common factor between all braces will be the presence of a bar connecting the shoes. The presence of a bar has been shown to be the crucial feature of clubfoot bracing (Janicki 2011). All caregivers will be instructed to place child in the FAB 23 hours a day for three months and then night time use (eight to twelve hours) hours a day for 2 versus 4 years based on treatment arm. All braces will include an implanted temperature logger that will be launched by the research coordinator prior to mounting.

All centers will provide the names and credentials of the orthotists they plan to work with for the study. The orthotist will adjust pads, areas of relief, and straps as needed to optimize fit. Clubfoot recurrence will be determined by the treating physician and treated with repeat casting followed by FAB use. Recurrence is defined as the development of any of the following deformities in isolation or in combination that require repeat cast application or surgical intervention: hindfoot varus, hindfoot equinus, forefoot adduction, forefoot cavus, or forefoot.

The Coordinating Center will develop manuals of operations to standardize patient management. However, variability in practices is allowed and will be at the discretion of the physician and orthotist at each clinical site. This may impart some variation in care across the centers, but will realistically mimic the current state of the art for the best care possible. Randomization within sites will minimize the potential bias introduced by differences in patient populations and management across sites and orthotists

4. Follow-Up Schedule

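### The primary analysis is cut one year after each arm's own end of bracing, with no stated time origin and no rule for recurrences during bracing; the plan needs both, plus an as-randomised comparison over a common horizon

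*Combined protocol and SAP*

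**What the plan says.** - **Cut-off.** Section 5 (Study Endpoint): "the data collected at 1-year follow-up post completion of treatment arms will be used for the primary analysis". The reason given is: "This ensures that patients in both treatment arms are followed for the same amount of time after they finish bracing". The same section notes that follow-up continues: "Although follow-up data will be collected for the duration of the trial".
- **Bracing.** Section 3 (Casting and Bracing Protocol) prescribes three months of near-full-time wear, then night-time wear "hours a day for 2 versus 4 years based on treatment arm". The primary cut is therefore at about year 3 v year 5 (3.25 v 5.25 if the three months are added).
- **Goal.** Aim 1a: "Establish the time dependent risk for relapse with need for further therapy in isolated clubfoot for 2 year versus 4 year bracing". Section 6 (Statistical Analysis): "The goal of this study is to establish the time-dependent risk for recurrence within the first year post-treatment". The sample size section states its goal in similar terms, and the Rationale gives the hypothesis that prolonged bracing reduces recurrence.
- **Methods.** The sample size section names a log-rank test on time to recurrence as the primary analysis. Section 6 adds Kaplan-Meier curves and a hazard ratio. Neither gives a starting point for the clock.
- **Recurrence.** Section 3 defines recurrence without limiting it to the time after bracing, and says: "Clubfoot recurrence will be determined by the treating physician and treated with repeat casting followed by FAB use". That describes management. It is not a rule for the analysis.
- **Analysis set.** Section 6 adopts intention to treat, "wherein patients will be included in the intervention group as determined by the randomization, independent of compliance".

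**The concern.** A time-to-event comparison needs a time origin, a horizon, and a rule for events before the origin. Here the horizon is tied to each arm's own treatment length and the other two are missing. A child who recurs in brace, is re-cast and is braced again also has no clear date of completion.

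The text supports two readings.

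*Clock from the end of bracing.* The goal statements in the sample size section and section 6 point this way. The children at risk are those recurrence-free for 2 years in one arm and for 4 in the other. That set is chosen after randomisation, and the arms are compared at different ages. Any natural fall in relapse risk with age is then credited to longer bracing. Arm labels are kept, but not every randomised child contributes.

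*Clock from about enrolment.* The sample size section expects complete data early in the curve, useful data from children who drop out, and follow-up beyond 12 months for many patients. These fit an early origin better. A child lost during bracing gives nothing to a clock that starts when bracing ends.

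At stake is whether the trial can answer its own hypothesis, and whether two analysts working from this plan would run the same primary test.

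**Working it through.** **1. The plan's own power figure.** Inputs from the sample size section and Table 1: 55 per arm, 10% v 31%, two-sided 5%, stated power 0.80.

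Power = Φ[(|p₁ − p₂| − 1.96·s₀)/s₁], where s₀ is the pooled and s₁ the unpooled standard error.

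- s₀ = √(0.205 × 0.795 × 2/55) = 0.0770
- s₁ = √((0.10 × 0.90 + 0.31 × 0.69)/55) = 0.0743
- Power = Φ[(0.21 − 0.1509)/0.0743] = Φ(0.795) = 0.787

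The same formula gives 0.990 for 10% v 45% and 0.963 for 10% v 40%. Table 1 (0.99, 0.96, 0.80) is reproduced. It assumes that all 55 completers per arm are at risk in the 12-month window.

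**2. Power if in-brace recurrences leave the risk set.** The yearly in-brace risks are assumptions.

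- 5% a year: 55 × 0.95² = 49.6 v 55 × 0.95⁴ = 44.8 at risk. With s₀ = 0.0840 and s₁ = 0.0795, power is about 0.72.
- 10% a year: 55 × 0.90² = 44.6 v 55 × 0.90⁴ = 36.1 at risk. With s₀ = 0.0922 and s₁ = 0.0854, power is about 0.63.

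**3. Rejection rate when bracing length has no effect.** Simulated first-relapse times, piecewise exponential with the same yearly risks in both arms; 55 per arm, no dropout, two-sided 5%. There were 10,000 replicates for the first and third tests and 20,000 for the second. All yearly risks are assumptions.

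| Risk in years 1-5 (%) | Log-rank, year after bracing | Log-rank from randomisation, cut at year 3 v 5 | Log-rank, all randomised, common 0-5 years |
|---|---|---|---|
| 10/10/10/10/10 | 4.7% | 5.1% | 4.9% |
| 15/12/10/8/7 | about 6% | 5.1% | 4.9% |
| 20/15/10/6/4 | 11.7% | 4.9% | 4.9% |
| 15/15/15/10/5 | 23.8% | 5.3% | 5.3% |
| 10/10/20/10/5 (extreme) | 47.7% | 5.0% | 4.8% |

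In the first test, most or all rejections favour 4 years once risk falls with age.

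**4. What the enrolment clock compares.** With each arm cut at its own point, no child in the 2-year arm is at risk after about year 3, so the log-rank uses years 0-3 only. Suppose stopping the brace mainly postpones relapse: 5% a year in brace, then 20%, 10% and 5% in the first three years off it. Five-year recurrence is 1 − 0.95² × 0.80 × 0.90 × 0.95 = 38% v 1 − 0.95⁴ × 0.80 = 35%. The own-cut log-rank rejects in 38% of trials, against 9% to a common year 5.

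Kaplan-Meier values read at each arm's own cut are not comparable either. At a flat 10% a year with no effect they are 1 − 0.9³ = 27% v 1 − 0.9⁵ = 41%.

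**5. What a common horizon costs.** Take 31% in year 3 for the 2-year arm and 10% in year 5 for the 4-year arm, with x% assumed in every other year.

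| x | Post-bracing-year log-rank | Common 0-5-year log-rank |
|---|---|---|
| 0% | 80% | 85% |
| 2% | 77% | 70% |
| 5% | 73% | 51% |
| 10% | 65% | 30% |

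The common horizon also gives the 2-year arm about three off-brace years against one. In three assumed cases where bracing only defers relapse, the common-horizon test favours 4 years in 24%, 33% and 57% of trials. The post-bracing-year test does so in about 2.4%.

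**The case against.** The strongest reply is that equal time off brace is deliberate. It guards against mistaking delay for prevention, which the common horizon does not do, as step 5 shows. That stands. It is why the post-bracing-year result should be kept and why the common horizon should not be imposed as the only basis for a claim.

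Three stronger readings are tempting, and the documents do not support them.

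- *A reader might infer that the primary analysis is certainly biased.* The sample size section gives real support to a clock near enrolment, and on that clock the named log-rank test holds its level. If risk is flat, the post-bracing clock holds it too.
- *A reader might infer that the plan breaks its intention-to-treat commitment.* Section 6 defines that commitment as analysis in the arm assigned, whatever the compliance. A post-bracing risk set keeps those labels. The valid criticism is that entry to the risk set depends on events after randomisation.
- *A reader might infer that counting in-brace recurrences reverses the bias, against the 4-year arm.* That takes a chi-square test on cumulative recurrence at year 3 v year 5, which rejects in 9-34% of trials in the five no-effect cases. The plan uses a dichotomous outcome for its power calculation only and names the log-rank test as primary. With that test the rate is about 5%.

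**Conclusion.** The concern holds as one of underspecification with a conditional consequence. It is certain that the primary cut is at about year 3 v year 5, and that neither the time origin nor the handling of in-brace recurrences is stated.

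The size depends on the reading and on yearly risks that the documents do not give. On the post-bracing clock, false rejection under no effect runs from about 5% (flat risk) through 6-24% (moderate declines) to about 48% (extreme). On the enrolment clock the level is right, but the comparison stops at year 3. The 0.80 row of Table 1 applies to a 12-month post-bracing comparison with 55 at risk per arm; it falls to about 0.72 or 0.63 if in-brace recurrences at 5% or 10% a year leave the risk set.

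Neither analysis alone settles whether assignment to longer bracing reduces recurrence, so the plan should define and report both. It should be changed before outcome data are examined.

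**What to change.** 1. In section 6, state the time origin and the handling of recurrences during bracing for each analysis.
2. Pre-specify an all-randomised, as-assigned log-rank test and Kaplan-Meier difference from randomisation to one common horizon of about 5 years, counting every first recurrence as section 3 defines it. Report it beside the post-bracing-year result. Make no claim that longer bracing reduces recurrence from the post-bracing-year result alone. Which of the two is primary is the sponsor's choice.
3. Keep the first year after bracing as a reported result, stating its risk set and the age difference between arms.
4. State that the common horizon gives the 2-year arm more off-brace time and cannot tell deferred from prevented relapse.
5. Reconcile the sample size section's follow-up beyond 12 months with the one-year cut in section 5, and state the comparison to which the Table 1 power applies.

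**Cost.** Text changes, one further analysis and a restated power figure. No new visits: the Crossovers, Dropouts section already keeps participants in study procedures to the study end, and the 4-year arm already needs about 5 years, so the read-out date does not move. There are two downsides. The common-horizon test may have lower power (step 5). There may also be extra loss in the 2-year arm after year 3: an uninformative 10% a year leaves the no-effect rejection rate at 4.8-5.2%, but informative loss would not be harmless.
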